5.2.1.4 Safety endpoints

The safety endpoints are as follows:

- AEs up to 8 weeks after EOT.
- SAEs up to 8 weeks after EOT.
- AEs leading to premature discontinuation of IMP.
- Clinically meaningful laboratory abnormalities up to 8 weeks after EOT.
- Changes from Baseline in laboratory parameters markers.
- Clinically meaningful ECG abnormalities up to 8 weeks after EOT.
- Clinically meaningful changes in vital signs from Baseline up to 8 weeks after EOT.
- Immunogenicity: presence of Ab to polyethylene glycol and pegcetacoplan peptide throughout treatment and follow-up periods.

5.3 Exploratory objectives

- To evaluate the PK of pegcetacoplan following twice-weekly s.c. infusions.
- To evaluate the effect of pegcetacoplan in complement biomarkers.

5.3.1 Exploratory endpoints

The exploratory endpoints are as follows:

- Pegcetacoplan PK concentrations at Week 24 and Week 48.
- Changes from Baseline to Week 24 and Week 48 in complement biomarkers (C3 levels, functional assays for classical and alternative complement pathways).
- Changes from Baseline through Week 24 and Week 48 in C3 deposition on RBCs by flow cytometry.
- Changes from Baseline to Week 24 and Week 48 in inflammatory biomarkers: TNF α , IL-6, IL-10, IFN γ and IL-1 β .
- Normalization of haptoglobin level at Week 24, Week 48 and Week 96.

- Time to first normalization from Baseline to Week 24 for haptoglobin level.

6 Investigational plan

6.1 Overall study design and plan

This is a phase 3, randomized, double-blind, placebo-controlled multicenter study of pegcetacoplan (1080 mg) or placebo, administered twice weekly by s.c. infusion in patients with CAD.

A total of 57 patients with CAD will be enrolled in this study. Patients will be randomized in a ratio of 2:1 to receive either pegcetacoplan or placebo, respectively. The randomization will be stratified by transfusion history (number of transfusions during the 6-month period prior to randomization ≥ 1 ; 0). Every effort should be made to enroll patients in both subgroups.

The planned length of participation in the study for each patient is a maximum of 110 weeks. This study will consist of 5 periods:

- Screening period: up to 4 weeks (may be extended by up to 2 additional weeks).
- Double-blind treatment period: 24 weeks (Part A).
- Open-label treatment period: 24 weeks (Part B).
- Open-label maintenance period: up to additional 48 weeks or until the product becomes commercially available (Part C).
- Follow-up period: 8 weeks.

The study design is outlined in Figure 1, and the visit schedule and planned assessments at each visit are detailed in Table 1 and Table 2.

No formal interim analyses are planned. However, data will be reported for Part A (double-blind treatment period) once all patients have completed their Week 24 visit (or have early discontinued) and the database has been cleaned and verified for all visits up to and including Week 24. Similarly, data will be reported after Part B (see Section 8.3.7).

6.1.1 Screening period (up to 4 weeks; may be extended by up to 2 additional weeks)

Informed consent will be obtained during a screening visit prior to any study-related procedures being conducted. Patients experiencing acute hemolytic crisis may receive blood cell transfusions during the screening period. The start of dosing must occur at least 7 days after receiving last transfusion.

Patients will be screened to confirm that entrance criteria for the study have been met. Key inclusion and exclusion criteria will be reviewed by the study medical monitor and eligibility

will be confirmed prior to the enrollment. If needed and after consultation with the medical monitor, the screening period may be extended by up to 2 additional weeks (e.g., eligibility laboratory results not available due to technical reasons or the patient receives an RBC transfusion during the last week of the screening period, reasonably reversible medical reasons such as COVID-19 infection).

6.1.1.1 Retesting and rescreening

Patients who fail to qualify for the study on the basis of certain laboratory parameters may be retested and/or rescreened at the discretion of the investigator.

6.1.1.1.1 Retesting

Retesting is defined as repeating laboratory tests within the same screening period.

Retesting is allowed due to technical issues (e.g., hemolysis, clotting). Patients who initially fail to qualify for the study on the basis of laboratory test results not meeting inclusion criteria may have, at the discretion of the investigator, any individual laboratory parameter retested 1 time within the 4-week (+2 weeks) screening period. Retesting within the 4-week (+2 weeks) screening period does not constitute rescreening; however, if retesting falls outside of the 4-week (+2 weeks) screening period, it should be considered rescreening (see below).

6.1.1.1.2 Rescreening

Rescreening is permitted for patients who consent to participate in the study but who do not initially meet all the requirements as outlined in the inclusion and exclusion criteria for reasons potentially reversible within a reasonable timeframe. In this case, agreement with the medical monitor should be obtained before conducting additional screening visits and/or repeat screening assessments to establish eligibility.

Screening is limited to 3 attempts (screening and 2 additional rescreening attempts).

In the event that rescreening occurs, the individual is required to reconsent and must be assigned a new identification number.

6.1.1.2 Screen failures

Screen failures are defined as patients who consent to participate in the clinical study but who do not meet 1 or more criterion required for participation and are not subsequently entered in the study (see Section 6.1.1.1.1 for retesting conditions). A minimal set of screen failure information is required to ensure transparent reporting of screen failure subjects, to meet the Consolidated Standards of Reporting Trials publishing requirements, and to respond to queries from regulatory authorities. Minimal information includes demography and reason for screen failure.

6.1.2 Double-blind treatment period (24 weeks): Part A

A total of 57 patients who meet all of the inclusion criteria and none of the exclusion criteria will be randomized in a 2:1 ratio to receive either pegcetacoplan or placebo.

Patients randomized into the study will receive IMP (pegcetacoplan or placebo) twice weekly for 24 weeks.

All standard-of-care medications can be continued, with the exception of protocol-defined prohibited medications (see Section 6.4.10.2).

During the double-blind treatment period, patients will receive a blood transfusion if their Hb level is ever shown to be < 7.0 g/dL. During this study period, transfusions will be considered, at the investigator's discretion, in symptomatic patients with Hb levels ≥ 7.0 and < 9.0 g/dL.

6.1.3 Open-label treatment period (24 weeks): Part B

All patients who complete the 24-week double-blind treatment period will be eligible to enter the open-label treatment period, in which they will receive pegcetacoplan 1080 mg twice weekly for up to 24 weeks (Week 48).

6.1.4 Open-label maintenance period (up to additional maximum 48 weeks or until the product becomes commercially available): Part C

After completion of the open-label treatment period, patients who benefit from therapy without significant side effects will continue receiving pegcetacoplan 1080 mg s.c. twice weekly for a maximum of 48 additional weeks or until the product is commercially available, whichever occurs first. In the event that the commercial product is not yet available at the end of Part C, patients will be managed outside of the current study on a case-by-case basis, in accordance with applicable laws and regulations.

At the end of the study, the sponsor will inform the investigators of the appropriate course of action based on the study results.

6.1.5 Follow-up period (8 weeks)

After completion of the open-label maintenance period, or if patients discontinue pegcetacoplan treatment early, an EOT visit will be performed, followed by an EOS visit 8 weeks later. See Figure 1 for the study schematic illustrating the study periods as a function of time.

6.1.6 Unscheduled visits

Unscheduled additional visits may be performed at the investigator's judgment. Any of the study procedures or other assessments may be performed at the unscheduled visit at the discretion of the investigator.

6.2 Discussion of study design, including the choice of control groups

In this double-blinded, randomized, phase 3 study, patients will be randomized in a ratio of 2:1 to receive pegcetacoplan or placebo. The study will enroll patients affected by CAD who have an Hb level \leq 9 g/dL. There are no currently approved therapies for patients with CAD in need of treatment; therefore, the choice of placebo as comparator is fully justified.

The primary endpoint of the study is a composite endpoint aimed at demonstrating a significant effect of pegcetacoplan on hemoglobin levels that is durable and effective in reducing transfusion requirement.

The treatment duration will be 24 weeks for both treatment groups to ensure capturing a durable treatment effect, with an extended 24-week open-label treatment period offered to all patients enrolled in the study, and 48 additional weeks to allow treatment continuity until the product is commercially available.

Patients will be considered as nonresponders if they require a rescue blood transfusion between Week 5 and Week 24 or who receive a prohibited concomitant medication or are withdrawn from treatment or lost to follow up before the end of the double-blind period .

6.3 Selection of study population

6.3.1 Inclusion criteria

A patient must fulfill the following criteria to be included in the study:

1. Age 18 years or older.
2. Diagnosis of primary CAD on the basis of the presence of all the following criteria at screening:
 - a. Signs of hemolysis with abnormal values for at least 2 of the following hemolytic markers:
 - i. Reduced haptoglobin level (< LLN).
 - ii. Elevated LDH level (> ULN).
 - iii. Elevated indirect bilirubin level (> ULN; > 3 x ULN for patients with Gilbert-Meilengracht syndrome).

iv. Increased ARC (above the ULN).

- b. Monospecific direct antiglobulin test strongly positive for C3d.
- c. Cold agglutinin titer ≥ 64 at 4°C .

3. Hb level ≤ 9 g/dL at screening.
4. An absolute neutrophil count ≥ 1500 cells/mm 3 at screening.
5. Documented results from bone marrow biopsy within 1 year of screening with lymphoproliferative infiltration $\leq 20\%$. Patients who have not received a bone marrow biopsy within 1 year of their screening visit or for whom bone marrow biopsy reports are incomplete or unavailable will be required to receive a bone marrow biopsy to determine eligibility.
6. Body weight ≤ 100 kg.
7. Either have vaccination against *S. pneumoniae*, *N. meningitidis* (Types A, C, W, Y, and B), and *H. influenzae* (Type B) within 2 years prior to screening or agree to receive vaccination during screening as follows:
 - First dose of vaccine against *N. meningitidis* Types A, C, W, and Y at least 2 weeks prior to start of study drug with second dose 2 months later (Study Day 57), and then boosters every 5 years.
 - First dose of the vaccine against *N. meningitidis* Type B at least 2 weeks prior to start of study drug with a second dose after at least 1 month (Study Day 29). First booster dose 1 year later, and then additional booster doses every 2 to 3 years.
 - *S. pneumoniae*: PCV13 and/or PPSV23 as per ACIP guidelines for adults or children with immunocompromising conditions.
 - *H. influenzae* Type B: 1 dose at least 2 weeks prior to start of study drug.

Vaccination is mandatory unless documented evidence exists that patients are nonresponders to vaccination. Vaccinations should be administered following the ACIP recommendations for adults or children with complement deficiencies and/or immunocompromising conditions.

8. WOCBP, defined as any women who have experienced menarche and who are NOT permanently sterile or postmenopausal, must have a negative pregnancy test at screening and agree to use protocol-defined methods of contraception for the duration of the study and 8 weeks after their last IMP dose.

Note: Postmenopausal is defined as having had 12 consecutive months with no menses without an alternative medical cause.
9. Men must agree to the following for the duration of the study and 8 weeks after their last IMP dose:
 - a. Avoid fathering a child.

- b. Use protocol-defined methods of contraception.
 - c. Refrain from donating sperm.
10. Willing and able to give written informed consent.

6.3.2 Exclusion criteria

The presence of any of the following will exclude a patient from inclusion in the study:

1. Have received other anticomplement therapies (approved or investigational) within 5 half-lives of the agent prior to randomization (e.g., eculizumab within 10 weeks, ravulizumab within 36 weeks or sutimlimab within 15 weeks) and are not able or willing to refrain from using them during the study. Patients previously treated with > 1 dose of sutimlimab will be excluded if they have not have experienced a documented increase in Hb \geq 1.0 g/dL during sutimlimab treatment.
2. Treatment with belimumab, rituximab or other anti-CD20 antibody (such as obinutuzumab or ocrelizumab), or with bendamustine, fludarabine, other cytotoxic drugs, or Bruton tyrosine kinase inhibitors such as ibrutinib, acalabrutinib and zanubrutinib, alone or in combination with rituximab within 16 weeks prior to randomization.
3. Use of prohibited medications as described in Section 6.4.10.2. Refer to Section 6.4.10.1 for the list of acceptable medications and required stable regimen periods for each.
4. Diagnosis of systemic lupus erythematosus or other autoimmune disease with antinuclear antibodies (antinuclear antibodies of long-standing duration without associated clinical symptoms will be adjudicated on a case-by-case basis by the investigator after discussion with the medical monitor).
5. History of an aggressive lymphoma or presence of a lymphoma requiring therapy.
6. Have received an organ transplant.
7. Cold agglutinin syndrome secondary to *Mycoplasma pneumoniae*, Epstein-Barr virus or other specific causative infection. In patients with long history of CAD, positive IgM titer and IgG titer without associated clinical symptoms will be adjudicated on a case-by-case basis by the investigator after discussion with the medical monitor.
8. HIV or hepatitis C virus detectable by polymerase chain reaction at screening or documented in the patient's medical record.
9. Chronic hepatitis B virus carriers with viral loads > 1000 IU/mL (> 5000 copies/mL) at screening or documented in the patient's medical record. Eligible patients who are chronic inactive carriers (≤ 1000 IU/mL) must receive prophylactic antiviral treatment (e.g., entecavir, tenofovir, lamivudine) according to local country guidelines.

10. Presence of an active malignant disease within the last 12 months other than skin basal cell carcinoma or in situ carcinoma of the cervix. A low-grade lymphoproliferative bone marrow disorder not requiring therapy by itself is not defined as a malignant disease in this context.
11. A monospecific direct antiglobulin test result of IgG > 1+.
12. Presence or suspicion of liver dysfunction as indicated by elevated ALT > 2.5 x ULN, or direct bilirubin levels > 2 x ULN. For any patient with increased direct bilirubin, the investigator should exercise medical judgement to ensure that the increased direct bilirubin value is due to hemolysis and discuss inclusion with the medical monitor. If the direct bilirubin is higher than the indirect bilirubin, in addition a thorough search for exclusion of underlying liver or cholestatic disease, including but not necessarily limited to abdominal ultrasound, is warranted to exclude liver and/or cholestatic disorders.
13. Hypersensitivity to pegcetacoplan or to any of the excipients or placebo compounds.
14. Known or suspected hereditary fructose intolerance.
15. Unresolved infection caused by encapsulated bacteria including *N. meningitidis*, *S. pneumoniae* and *H. influenzae*.
16. Presence or suspicion of severe recurrent or chronic infections that, in the opinion of the investigator, increase the patient's risk by participating in the study.
17. Participation in any other investigational drug trial or exposure to other investigational agent, device, or procedure within 30 days prior to screening period.
18. If breastfeeding, is unwilling to discontinue for the duration of study and for at least 8 weeks after the final IMP dose.
19. Inability to cooperate with study procedures.
20. Any disease(s), psychiatric condition, metabolic dysfunction, or findings from a physical examination or clinical laboratory test result that would cause reasonable suspicion of a disease or condition that may jeopardize the patient's wellbeing, that may increase the risk associated with study participation, that may affect the interpretation of the results, or that would make the patient unsuitable for this study.
21. Protected adults (guardianship, trusteeship) who are unable to express their consent and persons under court protection.
22. Any infection (including COVID-19) requiring hospitalization or treatment with intravenous anti-infectives not resolved within 2 weeks prior to the first dose of the IMP.

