Exclusion criteria:

1. Have received other anticomplement therapies (approved or investigational) within 5 half-lives of the agent prior to randomization (e.g., eculizumab within 10 weeks, ravulizumab within 36 weeks or sutiimlimab within 15 weeks) and are not able or willing to refrain from using them during the study. Patients previously treated with > 1 dose of sutiimlimab will be excluded if they have not experienced a documented increase in Hb ≥ 1.0 g/dL during sutiimlimab treatment.
2. Treatment with belimumab, rituximab or other anti-CD20 antibody (such as obinutuzumab or ocrelizumab), or with bendamustine, fludarabine, other cytotoxic drugs, or Bruton tyrosine kinase inhibitors such as ibrutinib, acalabrutinib and zanubrutinib, alone or in combination with rituximab within 16 weeks prior to randomization.
3. Use of prohibited medications as described in the protocol. The list of acceptable medications and required stable regimen periods are outlined in the study protocol.
4. Diagnosis of systemic lupus erythematosus or other autoimmune diseases with antinuclear antibodies (antinuclear antibodies of

long-standing duration without associated clinical symptoms will be adjudicated on a case-by-case basis by the investigator after discussion with the medical monitor).

5. History of an aggressive lymphoma or presence of a lymphoma requiring therapy.
6. Have received an organ transplant.
7. Cold agglutinin syndrome secondary to *Mycoplasma pneumoniae*, Epstein-Barr virus or other specific causative infection. In patients with long history of CAD, positive IgM titer and IgG titer without associated clinical symptoms will be adjudicated on a case-by-case basis by the investigator after discussion with the medical monitor.
8. HIV or hepatitis C virus detectable by polymerase chain reaction at screening or documented in the patient's medical record.
9. Chronic hepatitis B virus carriers with viral loads > 1000 IU/mL (> 5000 copies/mL) at screening or documented in the patient's medical record. Eligible patients who are chronic inactive carriers (\leq 1000 IU/mL) must receive prophylactic antiviral treatment (e.g., entecavir, tenofovir, lamivudine) according to local country guidelines.

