6.4.3 Method of assigning patients to treatment groups

Randomization will occur through the IRT system.

All patients who meet all the inclusion criteria and none of the exclusion criteria will be enrolled in the study after eligibility review by the study medical monitor, until such time that 57 patients have been enrolled in the study. Patients will then be randomly assigned through the IRT system to either pegcetacoplan or placebo in a 2:1 ratio. The randomization will be stratified according to number of transfusions during the 6-month period prior to randomization ≥ 1 ; 0. Every effort should be made to enroll patients in both subgroups.

Blinded IMP supplies labeled with kit numbers and other information as per Master Label and in line with regulatory requirements will be provided to each study site. IMP dosing will be initiated at the site after randomization. At each visit when IMP is administered and dispensed, the study staff will contact the IRT to obtain appropriate kit numbers.

For the open-label treatment and maintenance periods, all patients will receive pegcetacoplan open-label.

Please refer to the study manuals for further details of randomization and unblinding.

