6.4.10 Prior and concomitant therapy

6.4.10.1 Permitted concomitant therapy

All medications administered and procedures performed within 12 weeks before ICF signature will be recorded as prior medications and procedures. Medications administered and procedures performed from the time of informed consent through the EOS visit are regarded as concomitant and will be documented as such.

Concomitant medications refer to all treatment taken between the dates of the first dose of IMP and the end of the follow-up period, inclusive. Concomitant medication information must be recorded on the appropriate eCRF page. With the exception of prohibited medications any concomitant medications deemed necessary for the patient's standard of care or wellbeing during the study or for the treatment of any AE may be given at the discretion of the investigator. It is

the responsibility of the investigator to ensure that the details regarding all medications are recorded in full in the patient's eCRF.

The following concomitant medications are permitted only if administration is continued on a stable regimen (i.e., the dose has not changed for specific period defined below and is likely to remain unchanged during the study):

- Stable dosage for at least 4 weeks prior to randomization:
 - Erythropoietin.
 - Corticosteroids. If a patient, per the investigator's opinion, requires corticosteroids initiation during the study for reasons other than CAD, a discussion with the study medical monitor is required before starting treatment. Topical, inhalation or intraarticular use of corticosteroids is permitted.
 - Vitamin K antagonists (e.g., warfarin) with a stable INR.
 - Direct oral anticoagulants.
 - Iron supplements, vitamin B₁₂ or folic acid. If patients have previously received and tolerated iron chelation, this may be continued or reinitiated throughout the study if clinically indicated and upon discussion with the study medical monitor.
 - Low-molecular-weight heparin.
- Stable dosage for at least 8 weeks prior to randomization:
 - Immunosuppressants.

If clinically indicated and deemed in the best interest of the patient, the frequency or dose level of any of the above may be adjusted by the investigator in consultation with the study medical monitor.

COVID-19 vaccination is allowed during the study and should be administered according to the respective label.

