6.4.10.2 Prohibited medications

Other than pegcetacoplan, any therapy for CAD is prohibited during patient's participation in the study, including:

- Rituximab or any other anti-CD20 antibody (alone or in combination).
- Any other complement inhibitor (e.g., eculizumab, ravulizumab, or sutimlimab).
- Bortezomib
- Any other investigational drug.
- Plasma exchange.

Phlebotomy/venesection for iron overload is also prohibited during Part A of the study.

These medications are prohibited because they would interfere with the evaluation of the study endpoints. The use of prohibited medications during the study will require the patient to be permanently discontinued from the study treatment.

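### Does the conjunction in exclusion criterion 1 let patients inside the complement-inhibitor washout into the trial?

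*Protocol*

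**What the plan says.** The list in Protocol 6.3.2 works one criterion at a time: meeting any single one excludes. The first sentence of criterion 1 has two limbs. The first is treatment with another complement inhibitor "within 5 half-lives of the agent prior to randomization", with 10 weeks for eculizumab, 36 for ravulizumab and 15 for sutimlimab as examples. The second follows directly on the last example: "sutimlimab within 15 weeks) and are not able or willing to refrain from using them during the study". The synopsis uses the same conjunction: "and are not able or willing to refrain from using them during the study".

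The neighbouring rules are:

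- Criterion 2 gives its B-cell and cytotoxic washout with no second limb: "alone or in combination with rituximab within 16 weeks prior to randomization".
- Criterion 3 points to Protocol 6.4.10.2, which says "Other than pegcetacoplan, any therapy for CAD is prohibited during patient's participation in the study" and lists other complement inhibitors.
- Criterion 17 covers "exposure to other investigational agent, device, or procedure within 30 days prior to screening period".
- Under Protocol 6.4.3, patients who satisfy the criteria "will be enrolled in the study after eligibility review by the study medical monitor".

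**The concern.** If both limbs must hold, the washout never excludes by itself. A patient dosed shortly before randomization who agrees to stop would not meet criterion 1. The case is not fanciful: the second sentence of the same criterion sets a condition for patients previously given more than one dose of sutimlimab, so the trial expected some pretreated patients.

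At stake is the Baseline hemoglobin. It is the reference for the 1.5 g/dL response criterion and for the first key secondary endpoint, and residual complement inhibition on Day 1 could shift it. Carry-over could also reach into the transfusion-free period that forms part of the primary endpoint. With the per-protocol and sensitivity analyses dropped (SAP 1.1), no planned analysis sets such patients aside.

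**Working it through.** **1. The logic.** Let A be dosed within 5 half-lives before randomization, and B be unable or unwilling to refrain on study. As printed, criterion 1 excludes when A and B both hold.

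| A | B | Excluded by the first sentence as printed? |
|---|---|---|
| yes | yes | yes |
| yes | no | no (the gap) |
| no | yes | no (Protocol 6.4.10.2 bars the use itself) |
| no | no | no |

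**2. Does another rule restore the washout?** No. Criterion 3 with Protocol 6.4.10.2 concerns use during participation. Criterion 17 concerns investigational agents in the 30 days before screening. Neither sets a 5-half-life interval for an approved agent.

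**3. What the literal reading would leave.** Only patients in the first row would be excluded. They intend a use that Protocol 6.4.10.2 already prohibits, so the sentence would add almost nothing. The three windows would even narrow it, by letting a refuser with an older last dose escape the criterion. Reading the limbs as separate requirements is the only way to give the printed windows real work.

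**4. Timing.** Protocol 6.1 gives a maximum participation of 110 weeks, which reproduces only if extended screening is included: 6 + 24 + 24 + 48 + 8 = 110. Participation therefore starts in screening, and a complement inhibitor given after consent is already barred. The latest dose the protocol allows is at about consent.

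For a dose at consent and a screening period of s weeks, a window of W weeks ends at Study Week W − s:

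| Agent | W | s = 4 | s = 6 |
|---|---|---|---|
| Eculizumab | 10 | 10 − 4 = 6 | 10 − 6 = 4 |
| Sutimlimab | 15 | 15 − 4 = 11 | 15 − 6 = 9 |
| Ravulizumab | 36 | 36 − 4 = 32 | 36 − 6 = 30 |

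Screening may be shorter than 4 weeks, which moves these ends later, with Weeks 10, 15 and 36 as outer bounds. The first two bounds still fall before hemoglobin response is first judged at Week 16. The ravulizumab window covers Weeks 16, 20 and 24. SAP 7.1 counts transfusions from Day 29 (Study Week 4), so at s = 4 to 6 the overlap with that period is 0 to 2 weeks for eculizumab (4 − 4, 6 − 4), 5 to 7 for sutimlimab (9 − 4, 11 − 4), and all 20 weeks for ravulizumab (24 − 4). The exposure would thus not be confined to Baseline. These are times only; they say nothing about how many patients were affected, or whether any were.

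**5. Could such a patient be seen in the data?** Protocol 6.4.10.1 states: "All medications administered and procedures performed within 12 weeks before ICF signature will be recorded as prior medications and procedures". With 4 to 6 weeks of screening this reaches 12 + 4 = 16 to 12 + 6 = 18 weeks before randomization, leaving 36 − 16 = 20 to 36 − 18 = 18 ravulizumab weeks uncovered by that source. It is not the only source. Protocol 6.5.1 collects every earlier line of CAD treatment and states no such limit, and SAP 6.5 tabulates and lists prior CAD therapy. Whether last-dose dates are held there is not stated.

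**6. What a change could alter.** SAP 1.1 closes enrollment effective 10 January 2024, so a new sentence reaches nobody. A flag for recent use would be descriptive and would leave the ITT set, the exact test and the error rate as they are.

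**The case for a change.** The best case for acting runs as follows. The literal reading is one that a site could adopt: criterion 18, on breastfeeding, is a genuine exclusion conditional on willingness, and criterion 2 shows how a free-standing window is written in this list. Review by the medical monitor is a procedure and carries no window of its own. A recently dosed but willing patient breaks no rule as printed, so the deviation listing need not pick the patient up. A derived flag, with counts by arm, Baseline hemoglobin and responder status, would answer the question even if the answer were none.

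The textual part stands: the sentence is ambiguous and nothing else repairs it. The rest carries less weight. Nothing in the documents suggests that a site or the monitor applied the literal reading. Every patient needed hemoglobin of 9 g/dL or less and at least two abnormal hemolysis markers at screening, which narrows the route without closing it. Assignment was randomized, so recent use before randomization has no systematic tie to arm. The flag is also more than one column. It would need half-lives for agents beyond the three printed examples, which the documents do not give, and last-dose dates that may not exist. It would add a by-arm display to an analysis plan that was deliberately cut back, while the underlying listings are already planned (SAP 5.1 and 6.5).

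**Conclusion.** This is a clerical ambiguity, and correcting it now would gain nothing for the trial. The wording problem is certain; its consequence is not shown. No count, direction or size of effect follows from the documents, and neither the randomized patients nor the primary analysis would change.

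The judgement rests on two points: enrollment is closed, and the sentence's own windows make two separate requirements the probable intent. If the criterion were ever used for further enrollment, its two limbs would have to be reconciled in both places; this review does not say which eligibility rule is right. If last-dose dates are held, the study report could state whether anyone was dosed inside the window. That is a reporting preference and does not correct the plan.
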